8.34 Hypertension

Hypertension is a known AE associated with regorafenib treatment. Subject will have their blood pressure measured at least weekly during the first 5 weeks of treatment. If additional blood pressure measurements are done outside the study site, and the blood pressure is >140 mm Hg systolic or >90 mm Hg diastolic (NCI CTCAE v4.0), then the subject must contact study personnel. The management of hypertension, including the choice of antihypertensive medication, will be performed according to local standards and to the usual practice of the investigator. Every effort should be made to control blood pressure by medical means other than study drug dose modification. If necessary, Tables Section 8.1 and 8.2 outline suggested dose reductions.

Table 8.34: Management of Treatment-Emergent Hypertension		
Grade (CTCAE v4.0)	Antihypertensive Therapy	Regorafenib Dosing
1 Prehypertension (systolic BP 120 - 139 mmHg or diastolic BP 80 - 89 mmHg)	None	Continue regorafenib Consider increasing blood pressure (BP) monitoring
2 Systolic BP 140 - 159 mmHg or diastolic BP 90 - 99 mmHg, OR Symptomatic increase by >20 mmHg (diastolic) if previously within normal limits	Treat with the aim to achieve diastolic BP \leq 90 mm Hg: If BP previously within normal limits, start anti-hypertensive monotherapy If patient already on anti-hypertensive medication, titrate up the dose.	Continue regorafenib If symptomatic, hold regorafenib until symptoms resolve AND diastolic BP \leq 90 mm Hg ^a . When regorafenib is restarted, continue at the same dose level.
3 Systolic BP \geq 160 mmHg or diastolic BP \geq 100 mmHg OR More than one drug or more intensive therapy than previously used indicated	Treat with the aim to achieve diastolic BP \leq 90 mm Hg: Start anti-hypertensive medication AND/OR Increase current anti-hypertensive medication AND/OR Add additional anti-hypertensive medications.	Hold regorafenib until diastolic BP \leq 90 mm Hg, and if symptomatic, until symptoms resolve ^a When regorafenib is restarted, continue at the same dose level. If BP is not controlled with the addition of new or more intensive therapy, reduce by 1 dose level. If Grade 3 hypertension recurs despite dose reduction and antihypertensive therapy, reduce another dose level.
4 Life-threatening consequences (e.g., malignant hypertension, transient or permanent neurologic deficit, hypertensive crisis)	Per institutional guidelines	Discontinue therapy

- a. Patients requiring a delay of >4 weeks should go off protocol therapy
If BP remains controlled for at least one cycle. Patients requiring >2 dose reductions should go off protocol therapy.
- b. If BP remains controlled for at least one cycle, dose re-escalation permitted per investigator's discretion.
- c. Patients requiring >2 dose reductions should go off protocol therapy.

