- 3.23 Congestive heart failure $>$ New York Heart Association (NYHA) class 2.
- 3.24 Unstable angina (angina symptoms at rest), new-onset angina (begun within the last 3 months) or myocardial infarction less than 6 months prior to randomization.
- 3.25 Cardiac arrhythmias requiring anti-arrhythmic therapy. Note: Pace makers, beta

blockers or digoxin are permitted.

- 3.26 Uncontrolled hypertension. (Systolic blood pressure > 140 mmHg or diastolic pressure > 90 mmHg despite optimal medical management).
- 3.27 History of or current pheochromocytoma.
- 3.28 Arterial or venous thrombotic or embolic events such as cerebrovascular accident (including transient ischemic attacks), deep vein thrombosis or pulmonary embolism ≤ 6 months prior to randomization.
- 3.29a Ongoing infection > grade 2 NCI-CTCAE version 4.0.
- 3.29b Known history of chronic hepatitis B or C.
- 3.29c Patients with seizure disorder requiring medication.
- 3.29d Symptomatic metastatic brain or meningeal tumors unless the patient is > 6 months from definitive therapy, has a negative imaging study within 4 weeks of randomization and is clinically stable with respect to the tumor at the time of randomization. Note: Patient must not be undergoing acute steroid therapy or taper (chronic steroid therapy is acceptable provided that the dose is stable for one month prior to and following screening radiographic studies).
- 3.29e History of organ allograft (including corneal transplant).
- 3.29f Evidence or history of bleeding diathesis or any hemorrhage or bleeding event >CTCAE grade 3 ≤ 4 weeks prior to randomization.
- 3.29g Non-healing wound, ulcer, or bone fracture.
- 3.29h Renal failure requiring hemo-or peritoneal dialysis.
- 3.29i Dehydration CTCAE (version 4.0) grade ≥ 1 .
- 3.29j Substance abuse, medical, psychological or social conditions that may interfere with the patient's participation in the study or evaluation of the study results.
- 3.29k Known hypersensitivity to any of the study drugs, study drug classes, or excipients in the formulation.
- 3.29l Interstitial lung disease with ongoing signs and symptoms at the time of informed consent.
- 3.29m Persistent proteinuria of CTC Grade 3 or higher (≥ 3.5 g/24 hrs).
- 3.29n Patients unable to swallow oral medications.
- 3.29o Any malabsorption condition.
- 3.29p Unresolved toxicity greater than CTCAE (version 4.0) Grade 1 attributed to any

prior therapy/procedure excluding alopecia and oxaliplatin induced neurotoxicity \leq Grade 2.

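### Table 8.34: the Grade 3 hypertension hold is empty for an asymptomatic patient with systolic ≥160 and diastolic ≤90 mm Hg, because its release condition names diastolic pressure only

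*Combined protocol and SAP*

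**What the plan says.** Table 8.34 grades on either component of blood pressure. Grade 2 is "Systolic BP 140 - 159 mmHg or diastolic BP 90 - 99 mmHg" (or a symptomatic diastolic rise), and Grade 3 is "Systolic BP \geq 160 mmHg or diastolic BP \geq 100 mmHg". Grade 3 has one further route: "More than one drug or more intensive therapy than previously used indicated".

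The action columns are narrower. In both the Grade 2 and Grade 3 rows the antihypertensive instruction is "Treat with the aim to achieve diastolic BP" of 90 mm Hg or lower. The Grade 3 dosing instruction is "Hold regorafenib until diastolic BP" is 90 mm Hg or lower and, for a symptomatic patient, until the symptoms have gone. Regorafenib then restarts at the same dose level. At Grade 2 dosing continues unless the patient is symptomatic; a symptomatic hold ends when symptoms have gone and diastolic pressure is 90 or lower. No treatment aim and no release condition mentions systolic pressure.

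Two later steps refer to control of blood pressure without defining it: the first dose reduction in the Grade 3 row, and the footnote that permits re-escalation. The second reduction depends on Grade 3 recurring after a reduction.

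Elsewhere the protocol uses both components. Exclusion 3.26 describes uncontrolled hypertension as "Systolic blood pressure > 140 mmHg or diastolic pressure > 90 mmHg despite optimal medical management". The text of Section 8.34 asks patients to contact the site when an outside reading exceeds 140 systolic or 90 diastolic.

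**The concern.** A hold should be released on the measure that triggered it. Here the trigger can be systolic while the release is diastolic, so for one class of patients the hold is mandatory and already over on the same reading.

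Two things are at stake. The first is safety: a stated protective step does nothing for some of the patients it covers. Hypertension is among the events listed above 10% in Section 15.17, and the nursing guidance in Section 15.19 links blood pressure monitoring to the rare posterior leukoencephalopathy syndrome. The second is consistency. Section 8.0 requires the tables to be followed strictly in the first two cycles. One site could restart at once, as the table allows, while another waits for systolic pressure to fall. Doses given in those cycles feed the cumulative-dose and dose-intensity comparison in Section 16.44.

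**Working it through.** The plan states no figure on this point, so the check applies the Grade 3 rule as written to test readings.

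- Entry to Grade 3 by pressure: systolic ≥160 or diastolic ≥100.
- Release: diastolic ≤90 and no symptoms remaining.
- Minimum length of hold: none stated in the Grade 3 row. Footnote a sets only an upper limit, with patients needing more than 4 weeks going off protocol therapy.

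| Reading (mm Hg) | Symptoms | Grade 3? | Release already met at onset? |
|---|---|---|---|
| 175/85 | No | Yes (systolic) | Yes |
| 165/80 | No | Yes (systolic) | Yes |
| 165/90 | No | Yes (systolic) | Yes |
| 165/80 | Yes | Yes (systolic) | No, symptoms must resolve |
| 165/95 | No | Yes (systolic) | No, 95 > 90 |
| 165/99 | No | Yes (systolic) | No, 99 > 90 |
| 150/102 | No | Yes (diastolic) | No, 102 > 90 |
| 165/105 | No | Yes (both) | No, 105 > 90 |

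So, among patients graded by pressure, the hold is empty exactly when systolic is ≥160, diastolic is ≤90 and there are no symptoms. In that case the shortest hold the table permits is 0 days, and the reading on which dosing resumes is still Grade 3. The therapy-intensity route into Grade 3 is not needed for this result. Grade 2 does not show the same fault: without symptoms there is no hold to release, and with symptoms the hold lasts at least until they resolve.

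Next, the dose-reduction step for a patient who remains at 175/85 on added therapy:

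- Read against the table's only stated aim (diastolic ≤90): 85 ≤ 90, so pressure is controlled and no reduction follows.
- Read against exclusion 3.26 (systolic >140 or diastolic >90): 175 > 140, so pressure is uncontrolled and a one-level reduction follows.

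Both readings can be drawn from the protocol, and they lead to different doses.

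The other dose-modification tables provide a comparison. Table 8.31 delays a Grade 3 toxicity until it is Grade 2 or lower. The hand-foot table interrupts until Grade 0-1. Table 8.35 interrupts for transaminases above 5 × ULN until they fall below 3 × ULN or return to baseline. Each releases on the measure that caused the interruption.

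**The case against.** The best defence is that Section 8.34 leaves hypertension management to local standards and the investigator's usual practice, prefers medical control of pressure over changes to study drug, and calls the reductions suggested. A short hold fits that aim. The Grade 3 row also calls for starting, increasing or adding antihypertensives whichever component set the grade, so a systolic event is not left untreated. This stands, and it softens the practical effect. It does not supply a systolic release condition, and it sits beside the instruction in Section 8.0 to follow the tables strictly in cycles 1 and 2.

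A reader might go further in three ways that the documents do not support:

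- **That control is judged on diastolic pressure alone.** The table refers to blood pressure generally, and the protocol's only explicit description of uncontrolled hypertension, in 3.26, uses both components. The fair criticism is that the term is undefined in Table 8.34.
- **That systolic Grade 3 hypertension can never lead to a dose reduction.** A patient still at 175/85 on added therapy can reasonably be called uncontrolled. The second reduction uses recurrence of Grade 3, which includes the systolic limb, although it presupposes that the first reduction was made.
- **That every systolic-driven hold is empty.** The table of readings shows that symptomatic patients and those with diastolic 91 to 99 are effectively held.

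**Conclusion.** The point holds in its narrow form. For asymptomatic patients with systolic ≥160 and diastolic ≤90 mm Hg, the mandated Grade 3 hold is satisfied by the reading that triggers it. Separately, the first reduction step and the re-escalation footnote depend on an undefined term. Both follow from the text alone and need no assumption about event rates.

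The number of patients affected cannot be derived. Section 15.17 places hypertension above 10% but gives neither grade nor the share that is systolic only, so any count would rest on invented inputs. A reader might also infer harm to the primary endpoint. The documents do not show it: the same table governs both arms, and nothing connects holds in this subgroup with initiation of cycle 3 or with a bias between arms. No sample size or other stated statistical figure changes. Nor does the finding say that a diastolic criterion is clinically wrong, only that the table's columns do not agree.

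**What to change.** The sponsor should reconcile four pieces of wording in Table 8.34 and its footnotes: the Grade 2 and 3 definitions, the treatment aim, the hold-release conditions, and the meaning of controlled blood pressure. The release condition and the grading trigger should be consistent, and the result should be checked against 3.26 and the contact rule in Section 8.34. No threshold or clinical rule is proposed here; that choice belongs to the sponsor. A simple test of the revised table is whether, for an asymptomatic reading of 175/85, it gives one answer to each of three questions: is the patient held, what ends the hold, and does the pressure count as controlled.

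The cost is a few words in the next amendment. Blood pressure is already scheduled weekly through cycles 1 and 2 in Section 4.0, so no new visits or measurements are needed. The small downside is that some holds may change in length compared with the literal table.

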8.35 Liver Function Abnormalities

For patients with observed worsening of serum liver tests considered related to regorafenib (i.e. where no alternative cause is evident, such as post-hepatic cholestasis or disease progression), the dose modification and monitoring advice in Table below should be followed.

Regorafenib is a UGT1A1 inhibitor. Mild, indirect (unconjugated) hyperbilirubinemia may occur in patients with Gilbert's syndrome.

Table 8.35: Dose modifications/interruption for ALT and/or AST and/or bilirubin increases related to study drug			
Increases in ASL/ALT (per NCI-CTCAE v 4.0)	1st Occurrence	Restart	Re-occurrence
AST and/or ALT ≤ 5 X ULN (< Grade 3)	Continue dosing, with weekly monitoring of liver function until transaminases return to <3 X ULN (\leq Grade 1) or baseline.		
ALT and/or AST >5 X ULN (\geq Grade 3)	Interrupt dosing, with weekly monitoring until transaminases return to <3 X ULN or baseline.	If the potential benefit for reinitiating regorafenib/ placebo is considered to outweigh the risk of hepatotoxicity: Reduce one dose level and measure serum liver tests weekly for at least 4 weeks.	Discontinue
ALT and/or AST >20 X ULN (\geq Grade 4)	Discontinue		
ALT and/or AST >3 X ULN (\geq Grade 2) with concurrent bilirubin >2 X ULN	Discontinue treatment and measure serum liver tests weekly until resolution. Exception: patients with Gilbert's syndrome who develop elevated transaminases should be managed as per the recommendations outlined above for ALT/AST elevations.		
During the first 2 cycles of treatment, ALT, AST and bilirubin must be monitored every 2 weeks.			

8.4 No dose modifications expected for clobetasol propionate.

9.0 Ancillary Treatment/Supportive Care

- 9.1 Antiemetics may be used at the discretion of the attending physician.
- 9.2 Blood products and growth factors should be utilized as clinically warranted and following institutional policies and recommendations. The use of growth factors should follow published guidelines of the ASCO 2006 Update of Recommendations for the Use of White Blood Cell Growth Factors: An Evidence Based Clinical Practice Guideline. *Journal of Clinical Oncology*, Vol 24, No 19 (July 1), 2006: pp. 3187-3205.
- 9.3 Patients should receive full supportive care while on this study. This includes blood product support, antibiotic treatment, and treatment of other newly diagnosed or concurrent medical conditions. All blood products and concomitant medications such as antidiarrheals, analgesics, and/or antiemetics received from the first day of study treatment administration until 30 days after the final dose will be recorded in the medical records.
- 9.4 At first occurrence of PPES, independent of grade, prompt institution of supportive measures such as topical emollients, low potency steroids, or urea-containing creams should be administered.
- 9.41 Recommended prevention/management strategies for skin toxicities consistent with PPES are summarized below:

Control of calluses

Before initiating treatment with regorafenib:

- Check condition of hands and feet.
- Suggest a manicure/pedicure, when indicated.
- Recommend pumice stone use for callus or 'rough spot' removal.

During regorafenib treatment:

- Avoid pressure points.
- Avoid items that rub, pinch or create friction.

Use of creams

- Over the counter moisturizing creams or ointments are allowed, but patients cannot apply these within 1 hour before and after clobetasol applications.
- For grades 2 or 3, topical analgesics (e.g. lidocaine 5% patches, lidocaine/prilocaine cream TID, lidocaine 2-5% creams) are to be considered for pain control.
- Topical corticosteroids like clobetasol 0.05% should be instituted for subjects with Grade 2 or 3 PPES (in reactive arm). Avoid systemic steroids.
- For grade 2/3 Oral NSAIDs (celecoxib, ibuprofen) may be used for pain control
- Continue clobetasol during dose interruptions or decreased dosing/rechallenge
- Continue analgesia with topical analgesics or oral NSAIDs during dose interruptions or decreased dosing/rechallenge

Tender areas should be protected as follows:

- Use of thick socks/gloves to cover moisturizing creams
- Wear well-padded footwear
- Use insole cushions or inserts (e.g. silicon, gel)
- Foot soaks with tepid or cool water
- Use soft shoes or slippers (Crocs, TempurPedic slippers), avoid high heels and wood soles/heels

Suggested PPES Reaction Treatment

- CTCAE v4 Grade 1 ((Minimal skin changes or dermatitis (e.g., erythema, edema or hyperkeratosis) without pain)) - Continue regorafenib at current dose.
- CTCAE v4 Grade 2 ((Skin changes (e.g., peeling, blisters, bleeding, edema, or hyperkeratosis) with pain, limiting instrumental ADL (or intolerable grade 2, defined as grade 2 AE that does not decrease to grade ≤ 1 after 2 weeks of therapy OR that is considered intolerable per patient)) – See Section 8.33.
 - Oral (NSAIDs or narcotics) OR topical analgesia (lidocaine cream or patches PRN.
- CTCAE v4 Grade ≥ 3 ((Ulcerative dermatitis or skin changes with pain interfering with function. Severe skin changes (eg, peeling, blisters, bleeding, edema, or hyperkertosis) with pain; limiting self-care ADL)) – Interrupt regorafenib dose and monitor
 - Topical steroid cream BID AND topical anesthetics
 - Oral (NSAIDs or narcotics) OR topical analgesia (lidocaine cream or patches PRN.

- 9.5 Prevention/management strategies for diarrhea: Diarrhea can be a common side effect of regorafenib. The same dose-modification algorithm used for skin toxicities can be used to address these toxicities. However, the preventive/management strategies for diarrhea should be consistent with local standards (e.g., anti-diarrheals and optimized hydration status). Anti-diarrhea medications may be introduced if symptoms occur. Previous trials have shown that the diarrhea could be managed with loperamide. The recommended dose of loperamide is 4 mg at first onset, followed by 2 mg every 2 to 4 hours until diarrhea-free for 12 hours. In the event of grade 3 or 4 diarrhea, the following supportive measures are allowed: hydration, octreotide, and antidiarrheals.

Patients with severe diarrhea or any diarrhea associated with severe nausea or vomiting should be hospitalized for intravenous hydration and correction of electrolyte imbalances.

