8.0 Dosage Modification Based on Adverse Events

Strictly follow the modifications in the following tables for the first **two** cycles, until individual treatment tolerance can be ascertained. Thereafter, these modifications should be regarded as guidelines to produce mild-to-moderate, but not debilitating, side effects. If multiple adverse events are seen, administer dose based on greatest reduction required for any single adverse event observed. Reductions or increases apply to treatment given in the preceding cycle and are based on adverse events observed since the prior dose.

ALERT: *ADR reporting may be required for some adverse events (See Section 10)*

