8.3 Regorafenib Dose Modifications

Table 8.31 Recommended dose modification for toxicities except hand-foot-skin reaction, hypertension and ALT/AST/bilirubin			
NCI-CTCAE v4.0^a	Dose Interruption	Dose Modification^b	Dose for Subsequent Cycles
Grade 0-2	Treat on time	No change	
Grade 3	Delay until \leq Grade 2 ^c	Reduce by 1 dose level	If toxicity remains < Grade 2, dose re-escalation can be considered at the discretion of the treating investigator. If dose is re-escalated and toxicity (\geq Grade 3) recurs, institute permanent dose reduction.
Grade 4	Delay until \leq Grade 2 ^c	Reduce by 1 dose level. Permanent discontinuation can be considered at treating investigator's discretion.	
a. NCI-CTCAE = National Cancer Institute - Common Terminology Criteria for Adverse Events, version 4.0 b. Excludes alopecia, non-refractory nausea/vomiting, lymphocyte count decreased, non-refractory hypersensitivity and nonclinical and asymptomatic laboratory abnormalities. c. If no recovery after a 4 week delay*, treatment should be permanently discontinued unless subject is deriving clinical benefit. * Modify according to study specific cycle length			

If greater than 2 dose level reductions are required, regorafenib will be discontinued and the rest of the study follow up may be continued. The following tables outline dose adjustments for toxicities related to regorafenib except hand-foot skin reaction, hypertension and liver function test abnormalities.

The table above outlines dose adjustments for hematologic and non-hematologic toxicities related to regorafenib except PPES and hypertension. In addition to these recommended dose modifications, subjects who develop diarrhea, mucositis, anorexia or other events predisposing to fluid loss or inadequate fluid intake should be carefully monitored and rehydrated as clinically necessary. This is in order to minimize the risk of postural hypotension and renal failure.

	Grade 1	Grade 2	Grade 3
NCI-CTCAE v4.0 Palmar-plantar erythrodysesthesia syndrome	Minimal skin changes or dermatitis (e.g., erythema, edema, or hyperkeratosis) without pain	Skin changes (e.g., peeling, blisters, bleeding, edema, or hyperkeratosis) with pain	Severe skin changes (e.g., peeling, blisters, bleeding, edema, or hyperkeratosis) with pain

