Further description / examples of skin changes	Numbness, dysesthesia / paresthesia tingling, painless swelling, or erythema of the hands and/or feet	Painful erythema and swelling of the hands and/or feet	Moist desquamation, ulceration, blistering, or severe pain of the hands and/or feet
Effect on activities	Does not disrupt normal activities	Limiting instrumental activities of daily life (e.g., preparing meals, shopping for groceries or clothes, using the telephone, managing money)	Limiting self-care activities of daily life (e.g., bathing, dressing and undressing, feeding self, using the toilet, taking medications) and not bedridden
a. Palmer-plantar erythrodysesthesia syndrome is a disorder characterized by redness, marked discomfort, swelling, and tingling in the palms of hands or the soles of the feet.			

Grade of event (NCI-CTCAE v4.0)	Occurrence	Suggested Dose Modification
Grade 1	Any	Maintain dose level and immediately institute supportive measures for symptomatic relief
Grade 2	1 st occurrence	Consider decreasing dose by one dose level and immediately institute supportive measures. If no improvement, interrupt therapy for a minimum of 7 days, until toxicity resolves to Grade 0-1 ^{b,d}
	No improvement within 7 days or 2 nd occurrence	Interrupt therapy until toxicity resolves to Grade 0-1. When resuming treatment, treat at reduced dose level ^b
	3 rd occurrence	Interrupt therapy until toxicity resolves to Grade 0-1. When resuming treatment, decrease dose by one dose level. ^{b,d}
	4 th occurrence	Discontinue therapy
Grade 3	1 st occurrence	Institute supportive measures immediately. Interrupt therapy for a minimum of 7 days until toxicity resolves to Grade 0-1. ^c When resuming treatment, decrease dose by one dose level. ^{b,d}
	2 nd occurrence	Institute supportive measures immediately. Interrupt therapy for a minimum of 7 days until toxicity resolves to Grade 0-1. ^c When resuming treatment, decrease dose by one additional dose level. ^{b,d}
	3 rd occurrence	Discontinue treatment permanently.

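### Section 9.5 allows the skin-toxicity dose algorithm for diarrhea, but Table 8.31 already covers diarrhea with different Grade 2 and Grade 3 rules, and nothing says which prevails in cycles 1 and 2

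*Combined protocol and SAP*

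**What the plan says.** Section 8.0 opens with "Strictly follow the modifications in the following tables for the first" two cycles; after that the tables become guidelines.

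The title of Table 8.31 sets its scope: "Recommended dose modification for toxicities except hand-foot-skin reaction, hypertension and ALT/AST/bilirubin". Diarrhea is not among these exceptions, nor in the further exclusions of footnote b. The text below the table then names it: "In addition to these recommended dose modifications, subjects who develop diarrhea, mucositis, anorexia or other events predisposing to fluid loss" are to be monitored and rehydrated. Diarrhea is therefore inside Table 8.31.

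Section 9.5, under supportive care, says of diarrhea: "The same dose-modification algorithm used for skin toxicities can be used to address these toxicities". The only skin-toxicity dose algorithm in the protocol is the PPES table in Section 8.3. From a second Grade 2 occurrence, or if there is no improvement within 7 days, that table says: "Interrupt therapy until toxicity resolves to Grade 0-1. When resuming treatment, treat at reduced dose level".

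Section 8.12 takes Arm A patients off treatment when a reduction would go below 80 mg; Section 8.22 does the same for Arm B. Section 16.3 defines the primary endpoint as completing two cycles and starting cycle 3. Section 16.44 compares cumulative dose and dose intensity between arms over the first two cycles.

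**The concern.** One toxicity has two dose rules in exactly the period that the primary endpoint covers. One section requires strict adherence to the tables, and another makes a different algorithm available for an event that the tables already cover. A site that follows either can say it followed the protocol.

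Diarrhea is not a rare case here. Section 15.17 lists it among adverse events above 10%, and Section 10.51 has it graded at every evaluation. No blinding is described, so the investigator who picks the rule knows the arm. At stake are whether some patients remain on treatment to start cycle 3, and how much drug they receive in the two-cycle comparison.

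**Working it through.** **1. The two algorithms side by side, applied to diarrhea**

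| | Table 8.31 | PPES table, through 9.5 |
|---|---|---|
| Grade 2, first occurrence | No hold, no change | Reduction by one level to be considered; if no improvement, hold at least 7 days and to Grade 0-1 |
| Grade 2, no improvement in 7 days, or second occurrence | No hold, no change | Hold to Grade 0-1, resume at a reduced level |
| Grade 3 restart | At Grade 2 or lower, no minimum hold | After at least 7 days and at Grade 0-1 |
| Grade 3 dose on restart | One level lower | One level lower |
| Grade 4 | Has a row | No row, although 9.5 itself mentions Grade 4 diarrhea |

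**2. Where they converge.** From 160 mg, Table 8.31 takes a first Grade 3 event to 120 mg and a second to 80 mg. A third needs a third reduction, and the text below the table discontinues beyond two. The PPES table also stops at the third Grade 3 occurrence. At 80 mg, a Grade 3 event calls for a reduction under either table, so the patient leaves treatment either way. The tables also differ on re-escalation, but Sections 8.11 and 8.21 place re-escalation after week 8, outside the endpoint window.

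**3. Why the arms are not affected alike.** Take Grade 2 diarrhea that does not improve within 7 days.
- Arm A, still at the 80 mg starting dose: Table 8.31 changes nothing. The PPES table requires a reduced level on resuming, which is below 80 mg, so Section 8.12 ends treatment and the patient cannot start cycle 3.
- Arm B, at 160 mg: Table 8.31 changes nothing. The PPES table leads to 120 mg, with 80 mg still available.

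The Arm A route needs the patient to be at 80 mg when the reduction is called for; a patient already at 120 or 160 mg has a level left. Table 8.1 shows only a dash for significant toxicity at 80 mg, so it does not settle the case.

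**4. Two-cycle dose.** Planned doses come from Sections 7.11 and 7.12.
- Arm A: 7 × 80 + 7 × 120 + 7 × 160 + 21 × 160 = 560 + 840 + 1,120 + 3,360 = 5,880 mg.
- Arm B: 42 × 160 = 6,720 mg.
- A 7-day hold at 160 mg: 7 × 160 = 1,120 mg, which is 1,120/6,720 = 16.7% in Arm B and 1,120/5,880 = 19.0% in Arm A.
- A 7-day hold at 80 mg in Arm A: 560/5,880 = 9.5%.

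These figures assume that the hold falls on dosing days and that missed doses are not made up.

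**5. Scale for the primary endpoint.** The plan's own figure reproduces. For 45% against 63%, one-sided alpha 0.20 and 80% power, the continuity-corrected formula gives 54 per arm (108 in total, against 110 stated). The exact one-sided Fisher test at 55 per arm has power 80.4%. The sample size is not in question.

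The effect of the algorithm choice cannot be computed, because no diarrhea rate by grade is given. As an assumption only, suppose that it cost 2%, 5% or 10% of would-be completers (in Arm A, 0.63 × 55 = 34.65 expected, so about 0.7, 1.7 or 3.5 patients). Exact Fisher power would then be:

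| Loss falls in | 2% | 5% | 10% |
|---|---|---|---|
| Both arms | 79.3% | 77.6% | 74.6% |
| Arm A only | 76.5% | 69.8% | 57.3% |
| Arm B only (apparent power) | 83.0% | 86.4% | 91.0% |

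The rows show sensitivity, not an expected loss.

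**The case against.** The best defense is that the documents imply an order. Section 8.0 makes the tables strict in cycles 1 and 2, Table 8.31 covers diarrhea, and Section 9.5 is a permissive sentence in a supportive-care section. On that reading Table 8.31 governs and 9.5 adds little. The reading is reasonable, but the protocol does not state it. The PPES table is also one of the Section 8 tables, and 9.5 sends the reader there specifically for diarrhea.

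A second defense is that discretion exists anyway. Table 8.31 is headed as recommended and the PPES actions as suggested, a PPES footnote permits more conservative management, and Section 8.1 allows reduction for intolerable toxicity. This stands in part: reconciling 9.5 will not remove all discretion. It would remove a direct conflict with the instruction in 8.0.

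Some stronger readings are tempting but not supported:
- A reader might infer that the tables give different stopping rules for repeated Grade 3 diarrhea. They largely converge, as step 2 shows. The PPES stop at a fourth Grade 2 occurrence is distinct but unlikely to be reached in 8 weeks.
- A reader might infer that every Grade 2 episode costs a dose level or a week off under 9.5. The first-occurrence row only asks for a reduction to be considered, and holds only without improvement.
- A reader might infer that Grade 4 diarrhea has no rule. Table 8.31 has one; the gap arises only if the PPES table is used alone.

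**Conclusion.** The contradiction is real and should be corrected, but it is narrower than two wholly different regimes. It lies in the Grade 2 action, the Grade 3 restart threshold and the missing Grade 4 row, with no stated precedence.

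The main consequence for the primary endpoint is the Grade 2 route at 80 mg: the PPES table combined with Section 8.12 ends treatment for an Arm A patient where Table 8.31 would change nothing, while an Arm B patient at 160 mg has two levels left. Offering the option in both arms therefore does not make its effect equal.

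For the secondary dose comparison, one 7-day hold at 160 mg is worth 16.7% of Arm B's planned dose or 19.0% of Arm A's, on the assumptions in step 4. These are shares of dose. A reader might carry them over to the primary endpoint, but no section makes a hold or a 40 mg reduction a failure in itself.

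A reader might also conclude that the primary comparison is biased. The documents do not show that: they give no diarrhea rate and no indication of how often sites would use 9.5. The size of the effect is unknown.

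**What to change.** Reconcile Sections 8.0, 8.1, 8.3 (Table 8.31 and the PPES table) and 9.5 so that one named algorithm governs diarrhea at every grade, including Grade 4, in both arms during cycles 1 and 2. Remove the other reference, or turn it into a cross-reference to the named algorithm. State what the chosen rule means for an Arm A patient at 80 mg, where Table 8.1 has only a dash. Which algorithm applies is the sponsor's clinical decision.

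The cost is amendment wording. The sample size, the primary test and the endpoint definition do not change.
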